7.5 Handling of Partial Dates for Medications/Procedures/Therapy

When the start date or end date of a medication/therapy/procedure is partially missing, the date will be imputed to determine whether the medication/therapy/procedure is prior or concomitant. The following rules will be applied to impute partial dates for medications.

If the start date of a medication/procedure/therapy is partially missing, impute as follows:

- Medication/procedure/therapy start dates with a missing day and non-missing month will be assumed to have
 occurred on the first day of the non-missing month if the month and year is after first dose date. If the month and
 year are prior to the first dose date, the last day of the month will be assigned to the missing day. If the month and
 year are the same as the first dose date, the first dose date will be used.
- Medication/procedure/therapy start dates with missing day and month will be assumed to have occurred on the first day of the non-missing year (i.e., 01 January) if the year is after the year of first dose date. If the year is prior to the year of first dose date, December 31 will be assigned to the missing fields. If the year is the same as the year of the first dose date, the first dose date will be used.
- If the imputed start date > death date, then set to death date and report it as data issue

If the end date of a medication/procedure/therapy is partially missing, impute as follows:

- Medications/procedure that are not ongoing and have a medication/procedure/therapy stop date with a missing day and non-missing month will be assumed to have stopped on the last day of the non-missing month.
- Medications/procedure that are not ongoing and have a medication/radiotherapy stop date with a missing month will be assumed to have stopped on the last day of the non-missing year (i.e., 31 December).
- If the imputed end date > death date, then set to death date and report it as data issue.
- If the imputed end date is before imputed start date, report it as data issue.

If the year of the start date or the year of the end date of a medication/procedure/therapy is missing, or the start date or end date is completely missing, do not impute.

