7.4 Handling of Partial Dates for Adverse Events

If the year of the start date is missing or the start date is completely missing, the first dose date will be used. If the year of the end date is missing or the end date is completely missing, the event will be regarded as ongoing and do not impute. Impute AE end date first if both AE start date and end date are partially missing.

If end date of an adverse event is partially missing, impute as follows:

- If the day of the month is missing, the onset day will be set to the last day of the month.
- If the onset day and month are both missing, the day and month will be assumed to be December 31.
- If the imputed end date > death date, then set to death date.

If start date of an adverse event is partially missing, impute as follows:

- If the day of the month is missing, the onset day will be set to the first day of the month unless it is on or after the same month and year as study treatment. In this case, the onset date will be assumed to be the first dose date of treatment.
- If the onset day and month are both missing, the day and month will be assumed to be January 1 when the year is on or after the year of study treatment. If the year is prior to year of first dose, December 31st will be used. The event onset will be coded to the first dose date of treatment if year is the same as the year of first dose date to conservatively report the event as treatment-emergent.
- If the imputed AE start date is after the AE end date (maybe imputed), then update the AE start date with the AE end date as the final imputed AE start date.
- If the imputed start date > death date, then set to death date
- If the imputed end date is before imputed start date, the AE event will be treated as treatment emergent AE and report it as data issue.

Imputation of partial dates is used only to determine whether an event is treatment-emergent; data listings will present the partial date as recorded in the eCRF.

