7.7 Handling of Missing/Partial Dates for Prior Anticancer Therapy/Procedures

The following rules will be applied to impute partial dates such as prior systemic anticancer therapy or radiotherapy date (start/end date), or surgery date etc.

Impute end date first. If end date is partially missing, impute as follows:

• If both month and day are missing, then set to December 31

- If only day is missing, then set to the last day of the month
- For prior systemic therapy for cancer, if imputed end date > the first study drug date, then set to the first study drug date
- For prior radiotherapy, if imputed end date > the first study drug date, then set to the first study drug date 1

If start date is partially missing, impute as follows:

- If both month and day are missing, then set to January 01
- If only day is missing, then set to the first of the month
- If the imputed start date > end date, then set to the end date

If the year of start date or year of end date of a medication/therapy/procedure is missing, or the start date or end date is completely missing, do not impute.

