8.8 Prior and Concomitant Medications and Procedures

Prior and concomitant medications and procedures will be coded using the latest World Health Organization Drug (WHODrug) Dictionary version available. Unless specified otherwise, summaries of prior and concomitant medications will be presented by Anatomical Therapeutic Class (ATC) Level 2 and PT with numbers and percentages for subjects in the Safety Population.

A subject who takes more than one medication will be counted only once if these medications belong to the same ATC Level 2 classification.

In the summary tables, prior medications and concomitant medications and procedures will be presented by decreasing frequency of subjects overall within each ATC Level 2 class and then similarly by decreasing frequency of subjects overall within each preferred term. In cases of ATC Level 2 classes or preferred terms with equal frequencies, medications will be sorted alphabetically.

Prior medications/procedures are defined as those medications/procedures that started prior to the first administration of the study drug. Concomitant medications/procedures are defined as those medications/procedures taken on or after the first administration of the study drug till 30 days after the last dose of study treatment, or the start of subsequent anticancer therapy, whichever occurs first.

A prior medication/procedure could also be classified as "both prior and concomitant medication/procedure" if the end date is on or after first dose of study treatment. In the listing, it will be indicated whether a medication is prior-only, concomitant-only, or both prior and concomitant medication.

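### SAP 7.5 can give a medication or procedure a start date after its own stop date, so a course that ended before first dose is not classed as prior

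*SAP*

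**What the plan says.** The purpose of the imputation is stated at the top of SAP 7.5: "the date will be imputed to determine whether the medication/therapy/procedure is prior or concomitant". Two branches matter here.

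- Day missing: where the month and "year are the same as the first dose date, the first dose date will be used".
- Day and month missing: "If the year is the same as the year of the first dose date, the first dose date will be used".

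The only rule in 7.5 that compares the two ends of a record is "If the imputed end date is before imputed start date, report it as data issue".

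SAP 8.8 then assigns the class: "Prior medications/procedures are defined as those medications/procedures that started prior to the first administration of the study drug". Concomitant items are those "taken on or after the first administration of the study drug till 30 days after the last dose of study treatment" or until subsequent anticancer therapy begins, if that is sooner. A record that is already prior becomes both prior and concomitant if it ends on or after first dose. The listing must show prior-only, concomitant-only or both.

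Two neighbouring sections handle the same situation differently. SAP 7.4, for adverse events: "If the imputed AE start date is after the AE end date (maybe imputed), then update the AE start date" to the end date. SAP 7.7, for prior anticancer therapy and procedures, imputes the end date first and then says: "If the imputed start date > end date, then set to the end date".

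**The concern.** A partial start combined with a known earlier stop is a consistent record: the course began at some unknown time and was over before dosing. The two branches of 7.5 ignore the stop and place the start on the first dose date. The imputation rule itself creates the contradiction, not the data.

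The class then goes wrong. A start equal to the first dose date is not before it, so the record is not prior under 8.8. The stop date cannot rescue it, because 8.8 uses the stop only to extend an already prior record to both. Prior-only, the correct entry in the listing, cannot be reached.

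The schedule of activities counts transfusions and growth factors among concomitant medications and procedures. Neutropenia is an anticipated toxicity (protocol synopsis), so safety readers will look at marrow-support records closely, and cohorts at each dose level are small. What is at stake is the accuracy of those descriptive displays.

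**Working it through.** The plan gives no figure to reproduce. The check applies the 7.5 and 8.8 rules literally to test records, and then repeats them with the cap used in 7.4 and 7.7.

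**Inputs**

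- First dose date: 20 March 2025 (assumed, for illustration).
- Start (7.5): a missing day in the first-dose month, or missing day and month in the first-dose year, becomes the first dose date. A missing day in an earlier month becomes the last day of that month. Missing day and month in an earlier year becomes 31 December.
- End (7.5): a missing day becomes the last day of the month.
- Prior (8.8): start < first dose.
- Cap: start = min(imputed start, recorded or imputed end).

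**Results**

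| Recorded start | Recorded stop | Start as written | End | Prior as written? | Start with cap | Prior with cap? |
|---|---|---|---|---|---|---|
| day unknown, Mar 2025 | 10 Mar 2025 | 20 Mar 2025 | 10 Mar 2025 | no | 10 Mar 2025 | yes |
| 2025 only | 15 Feb 2025 | 20 Mar 2025 | 15 Feb 2025 | no | 15 Feb 2025 | yes |
| 2025 only | day unknown, Feb 2025 | 20 Mar 2025 | 28 Feb 2025 | no | 28 Feb 2025 | yes |
| day unknown, Feb 2025 | 10 Feb 2025 | 28 Feb 2025 | 10 Feb 2025 | yes | 10 Feb 2025 | yes |
| 2024 only | 10 Nov 2024 | 31 Dec 2024 | 10 Nov 2024 | yes | 10 Nov 2024 | yes |
| day unknown, Mar 2025 | day unknown, Mar 2025 | 20 Mar 2025 | 31 Mar 2025 | no | 20 Mar 2025 | no |

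Rows 1 to 3 are the fault: the end precedes the start, prior status is lost, and the cap restores prior-only. In rows 1 and 2 the stop is fully recorded, so the data-issue rule, worded for imputed end dates, does not literally reach them. In row 3 it does, but it changes neither date nor class.

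Rows 4 and 5 set one limit: starts in an earlier known month or year stay prior, although their imputed start also falls after the stop. Row 6 sets another: if the stop lacks its day in the first-dose month, the end goes to month end, no conflict appears, and the cap changes nothing.

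**How often could the calendar condition be met?** Assume one-day events spread evenly over the 28 days before first dose, and first-dose dates spread evenly over 2025. For a first dose on day d of a month, min(d − 1, 28) of the 28 preceding days share its month. The sums over d are 462 for a 31-day month, 434 for a 30-day month and 378 for February.

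- Same month: (7 × 462 + 4 × 434 + 378) / (365 × 28) = 5,348 / 10,220 = 52%.
- Same year: (378 + 28 × 337) / 10,220 = 9,814 / 10,220 = 96%.

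These shares apply only to records that already have the relevant partial start (day missing for 52%, day and month missing for 96%) and a known stop before dosing. Longer courses may have begun in an earlier month or year, so their shares are lower. The documents do not say how many such records there will be.

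**The case against.** The strongest reply is that 8.8 defines concomitant by use. A course known to have stopped before first dose was not taken on or after it, so it is not concomitant on that wording. A reader might infer that pre-treatment marrow support will be tabulated as on-treatment support. The text does not establish that: it would happen only if a programmer classed records on the imputed start alone. What the text does show is loss from the prior class.

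A reader might also infer that a QT-prolonging drug or a P-gp/BCRP inhibitor properly stopped before dosing (Exclusions 17 and 18) would look like a protocol deviation. The documents do not support this. SAP 7.5 confines the imputation to the prior/concomitant decision, and SAP 8.3 has deviations identified and classified before any snapshot or lock, with no mention of imputed dates.

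Nor should the gap between stop and imputed start be pictured as many months. The schedule of activities collects these records from the Screening Visit, and Screening runs from Day -28 to Day -1. Inclusion 12a also bars transfusions and growth factors within 7 days of first dose. For those items the relevant stops lie at roughly Day -28 to Day -8.

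Transfusions are a weak example in any case. They are usually one-day events, so a fully known stop also gives the start, and when the day is missing from both dates in the first-dose month, row 6 applies.

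Two defences do not stand. The data-issue rule shows that the plan expects such contradictions, but it corrects nothing. And treating an unknown start as concomitant is a sensible default only while timing is uncertain; a stop before dosing removes that uncertainty.

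**Conclusion.** The point holds, as a minor one. For a partial start in the first-dose month, or a year-only start in the first-dose year, with a recorded or imputed stop before first dose, 7.5 produces a start after the stop. The record then fails the 8.8 definition of prior. It lands in neither class, or in concomitant under start-date-only programming, when prior-only is correct. This follows from the wording and needs no assumption about the data.

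The size is limited. Only descriptive prior/concomitant tables and listings are affected; the primary endpoint of treatment-emergent adverse events, DLTs and dose decisions are not. The number of records is not given and is probably small, mainly multi-day non-anticancer drugs, including growth factors, stopped shortly before dosing. Prior systemic anticancer therapy, radiotherapy and surgery fall under 7.7, which has the cap.

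**What to change.** Add to SAP 7.5: impute the end date first; where the imputed start then falls after the recorded or imputed end, set the start equal to the end; class any record that ended before first dose as prior-only. The first two steps are the convention of 7.7, and 7.4 uses the same cap. The third makes the 8.8 class explicit for these records. The cost is a short addition to the SAP and about one line of code, with no new data. The cap also removes the impossible date order in records that are already classed correctly, such as rows 4 and 5, without changing their class.

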7.6 Handling of Missing/Partial Dates during Screening Visit

The following rules apply to partially missing dates recorded during the screening visits (e.g. initial diagnosis), If date is completely missing, no imputation is needed:

- If the day of the month is missing, the first day of the month will be used if the year and the month are the same as the first dose of study days. Otherwise, the 15th will be used.
- If the day and month are both missing, the day and month will be assumed to be January 1 when the year is on the year of study treatment. If the year is prior or after the year of first dose date, the date of the first of July will be used, unless other data indicates the date is earlier.

7.7 Handling of Missing/Partial Dates for Prior Anticancer Therapy/Procedures

The following rules will be applied to impute partial dates such as prior systemic anticancer therapy or radiotherapy date (start/end date), or surgery date etc.

Impute end date first. If end date is partially missing, impute as follows:

• If both month and day are missing, then set to December 31

- If only day is missing, then set to the last day of the month
- For prior systemic therapy for cancer, if imputed end date > the first study drug date, then set to the first study drug date
- For prior radiotherapy, if imputed end date > the first study drug date, then set to the first study drug date 1

If start date is partially missing, impute as follows:

- If both month and day are missing, then set to January 01
- If only day is missing, then set to the first of the month
- If the imputed start date > end date, then set to the end date

If the year of start date or year of end date of a medication/therapy/procedure is missing, or the start date or end date is completely missing, do not impute.

7.8 Handling of Missing/Partial dates for Post-study Anticancer Therapy/Radiotherapy

For records with completely missing start date, end of treatment date will be used as the start date of post-study therapy/radiotherapy. If the start date of post-study anticancer therapy/radiotherapy is partially missing, impute as follows:

- If the day of the month is missing, the start day will be set to the last day of the month unless it is on the same month and year as last dose of the study treatment. In this case, the start date will be assumed to be the last dose date + 1.
- If the day and month are both missing, the start date will be set to January 1st unless it tis on the same year as the last dose date of the study treatment. In this case, the start date will be assumed to be the last dose date + 1.
- If only month is missing, year and day are present, set the missing month to the month of the last dosing date of the study drug unless the day is prior to the last dose day. In this case, impute the missing month as the month of last dose date + 1

No imputation is needed for post-study therapy/radiotherapy end date.

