5.2 Primary Endpoints

• Incidence and severity of treatment-emergent adverse events (TEAEs)

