12.2 Adverse Events

All reported AEs will be coded using the MedDRA with the most current version for the purposes of summarization. NCI CTCAE Version 5.0 will be used for grading AEs. AEs will be collected and recorded for each patient from the day of signing the ICF until 30 days after last trial intervention administration or until participant started alternative anticancer

therapy, whichever is sooner. Prior to receiving trial intervention, only AEs considered related to trial procedures, and all serious adverse events (SAEs) will be summarize by study phase and treatment arms.

A treatment-emergent adverse event (TEAE) will be defined as any event that was not present prior to the initiation of trial intervention(s) or any event that worsens in either intensity or frequency following exposure to trial intervention(s) through 30 days after cessation of trial treatment or until the participant starts alternate anti-cancer therapy, whichever is sooner, with exception of treatment related SAEs which were reported until the end of survival follow-up and will be included as TEAE regardless of time of onset.

All TEAEs reports will summarize by dose levels and dose schedules unless otherwise specified.

Overall TEAE summaries will be presented for the Safety Population. The summaries will include the following categories:

- All TEAEs
- TEAE by CTCAE grade
- TEAEs with CTCAE Grade ≥ 3
- TEAE leading to study treatment discontinuation
- TEAE leading to death
- TEAE related to study treatment
 - TEAEs related to study treatment are defined as 'definitely related', 'probably related', or 'possibly related', to study drug as assessed by the Investigator.
- TEAE related to study treatment with CTCAE Grade ≥ 3
- TEAE related to study treatment leading to treatment discontinuation
- TEAE related to study treatment leading to study treatment interruption
- TEAE related to study treatment leading to study treatment reduction
- TEAE related to study treatment leading to death
- Serious TEAE
- Serious TEAE leading to treatment discontinuation
- Serious TEAE leading to death
- Serious TEAE related to study treatment
- Serious TEAE related to study treatment leading to study treatment discontinuation
- Serious TEAE related to study treatment leading to death

Any missing onset date, causality, or severity must be queried for resolution. Unresolved missing causality will be handled according to the following rules:

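### SAP 7.8 can date subsequent anticancer therapy too early when its start date is incomplete, closing the 30-day TEAE window and removing eligible events from the primary endpoint tables

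*SAP*

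**What the plan says.** The primary safety endpoint in SAP 5.2 is the incidence and severity of TEAEs. SAP 12.2 fixes the end of the TEAE window: "through 30 days after cessation of trial treatment or until the participant starts alternate anti-cancer therapy, whichever is sooner". It makes one exception, for "treatment related SAEs which were reported until the end of survival follow-up and will be included as TEAE regardless of time of onset". Sites collect adverse events under a matching rule, "until 30 days after last trial intervention administration or until participant started alternative anticancer" therapy. The start of the next therapy therefore decides whether a post-treatment event is a TEAE.

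SAP 7.8 says how to fill in that start date when it is incomplete:

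- Completely missing: "For records with completely missing start date, end of treatment date will be used as the start date of post-study therapy/radiotherapy".
- Day unknown: "the start day will be set to the last day of the month unless it is on the same month and year as last dose". For the same-month case the rule is: "In this case, the start date will be assumed to be the last dose date + 1".
- Day and month missing: 1 January of the recorded year, or last dose + 1 if that is the year of the last dose.
- Month alone missing: the recorded day is kept, in the month of the last dose or, if that day is earlier than the last-dose day, the following month.

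Nothing in SAP 7.8 or 12.2 exempts the TEAE cut-off from these rules. SAP 8.8 also ends the concomitant-medication window at the start of subsequent anticancer therapy.

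**The concern.** For a window that closes when new therapy starts, an early imputed start is the anti-conservative choice. An event with a fully known onset, which the site collected because no new therapy had begun, can be classed as not treatment-emergent only because the therapy date was recorded as a month or a year.

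Elsewhere the SAP leans the other way. SAP 7.4 imputes an uncertain event onset "to conservatively report the event as treatment-emergent", and SAP 12.2 treats unresolved missing causality as related. SAP 7.4 cannot rescue the events at issue here, because their onset dates are not missing.

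At stake are non-serious events, including related Grade 3 events, and serious events or deaths judged unrelated. Toxicity after stopping would be understated in participants who stop and switch treatment.

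**Working it through.** **Inputs.** The 30-day limit and the therapy cut-off come from SAP 12.2, and the imputation branches from SAP 7.8. SAP 4.2 places the EOT visit within 7 days after last dose. The documents give no distribution for the true start of new therapy, so it is assumed uniform over 1–30, 1–60 or 1–90 days after last dose, for every last-dose date in 2025.

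**Formula.** With L the last dose and S the start of new therapy, the post-treatment window in days is W = max(0, min(30, S − L)). For any true start 30 or more days after last dose, W = 30, which is the plan's own figure.

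**Window by branch of SAP 7.8.**

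| Recorded start | Imputed start | W |
|---|---|---|
| Nothing | End of treatment date | 0 if this is last dose; up to 7 if it is the EOT visit |
| Month and year, same as last dose | L + 1 | 1 |
| Month and year, later month | Last day of that month | 28–30; never shorter than the true window |
| Year only, same as last dose | L + 1 | 1 |
| Year only, following year | 1 January | 30 for L = 2 December, 17 for 15 December, 1 for 31 December |
| Day and year only | First such day after last dose | Varies: L = 10 June, true start 25 July gives 25 June, W = 15 instead of 30 |

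**Example 1.** Last dose is 3 March, therapy is recorded as March, and a Grade 3 non-serious event starts on 10 March. The imputed start is 4 March, so W = 1 and the event is not a TEAE. If therapy really began on 31 March, W should be 28, so 27 days are lost.

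**Example 2.** Last dose is 25 March. Therapy recorded as March gives W = 1. Therapy recorded as April is imputed to 30 April, which is 36 days later, so W = 30. The true starts could be 31 March and 1 April.

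**Share of incomplete records whose window falls from more than 1 day to 1 day:**

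| True start uniform over | Day missing | Day and month missing |
|---|---|---|
| 1–30 days | 46% | 93% |
| 1–60 days | 23% | 90% |
| 1–90 days | 15% | 87% |

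For day-missing records, a similar share (48%, 24%, 16%) has its window lengthened by the month-end rule.

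**Mean days lost when the date is completely missing.** Let k be the true start in days after last dose.

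- If end of treatment means last dose, the loss is min(30, k): 465/30 = 15.5; (465 + 30 × 30)/60 = 22.8; (465 + 60 × 30)/90 = 25.2.
- If it means an EOT visit at day 7, the loss is max(0, min(30, k) − 7): 276/30 = 9.2; (276 + 30 × 23)/60 = 16.1; (276 + 60 × 23)/90 = 18.4.

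**The case against.** SAP 7.8 does not state its purpose, and SAP 12.2 does not cite it. The efficacy section is not visible, so the early dates may have been written for use there. This stands as a limit on certainty: the link to the TEAE window is an inference. But 7.8 is the only visible rule for this date, and nothing restricts its use.

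The trial's procedures should also make incomplete dates less common. The notes to the SAP 14.1.1 schedules require start and stop dates of post-trial anticancer therapy and place the EOT visit before the next therapy. SAP 4.2 adds a safety visit about 30 days after last dose. On the other hand, survival follow-up runs about every 90 days and may be by telephone, so partial dates remain plausible. The documents do not say how often they occur.

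Four stronger readings are tempting and are not supported:

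- That every partial date is pulled back to last dose + 1. A day-missing date in a later month goes to month end; the later-year and month-only branches follow other rules.
- That a completely missing date always leaves 0 days. SAP 8.9.1 takes last dose as the treatment end date, but only for exposure duration. If SAP 7.8 means the EOT visit, up to about 7 days remain.
- That the events vanish. They leave the TEAE tables but stay in the listing of all adverse events. Treatment-related serious events, on-treatment TEAEs and the DLT window are not affected.
- That a number of participants can be stated. Any percentage applied to the planned 80 would be a guess. It would also count incomplete dates, not lost events: a lost event must begin or worsen after the imputed date, before the true start and within 30 days, and must not be a treatment-related serious event.

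Finally, the SAP 7.4 phrase concerns event onset dates, not therapy dates. The two sections differ in direction; they do not formally contradict each other.

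**Conclusion.** The point holds for specific branches. The window can close early when the start date is completely missing, when only the day is missing and the month is that of the last dose, and when only the year is known and is that of the last dose. A year-only date in the following year can also shorten it when the last dose falls in December.

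In the two last dose + 1 branches, 1 day is left of up to 30. In the completely missing branch, 0 to about 7 days are left. The error favours the drug on the primary safety endpoint, but its effect on TEAE incidence cannot be sized from the documents. The conclusion assumes that SAP 7.8 feeds the cut-off in SAP 12.2. The percentages and mean losses also rest on the assumed uniform start times. The SAP should be changed because the direction is wrong for safety and the remedy is cheap.

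**What to change.** Add to SAP 7.8 a separate safety cut-off date for the TEAE window in 12.2 and, for consistency, the concomitant-medication window in 8.8:

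- If part of the date is known, use the latest date consistent with it (last day of the known month, or 31 December of the known year), capped at last dose + 30 days.
- If the date is completely missing, let the window run the full 30 days.
- Define *end of treatment date*, and limit the existing early dates to non-safety uses.

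With last dose on 10 June and therapy recorded as June, the window becomes 20 days instead of 1. With only that year recorded, or nothing recorded, it becomes 30 days instead of 1, or instead of 0 to about 7.

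The cost is SAP wording and one extra derived date. A few events that began after the true start of new therapy may be counted as TEAEs. The 30-day cap limits this, as does the rule that routine event collection stops once the new therapy has actually started.
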